#### **8.2.2 Serious adverse events (SAEs)**

A serious adverse event is any untoward medical occurrence or effect that at any dose: Results in death; is life threatening (at the time of the event); requires hospitalisation or prolongation of existing inpatients' hospitalisation; results in persistent or significant disability or incapacity; is a congenital anomaly or birth defect.

Any other important medical event that may not result in death, be life threatening, or require hospitalization, may be considered a serious adverse experience when, based upon appropriate medical judgement, the event may jeopardise the subject or may require an intervention to prevent one of the outcomes listed above.

SAE will be reported by the participating centres, preferably by mail, as soon as possible to the coordinating investigator.

The coordinating investigator will report the SAEs through the web portal *ToetsingOnline* to the accredited METC that approved the protocol, within 15 days after the coordinating investigator has first knowledge of the serious adverse events.

SAEs that result in death or are life threatening should be reported expedited. The expedited reporting will occur not later than 7 days after the responsible investigator has first knowledge of the adverse event. This is for a preliminary report with another 8 days for completion of the report.

### 8.2.3 Suspected unexpected serious adverse reactions (SUSARs)

Adverse reactions are all untoward and unintended responses to an investigational product related to any dose administered.

Unexpected adverse reactions are SUSARs if the following three conditions are met:

the event must be serious (see chapter 9.2.2); there must be a certain degree of probability that the event is a harmful and an undesirable reaction to the medicinal product under investigation, regardless of the administered dose the adverse reaction must be unexpected, that is to say, the nature and severity of the adverse reaction are not in agreement with the product information as recorded in: Summary of Product Characteristics (SPC) for an authorised medicinal product or Investigator's Brochure for an unauthorised medicinal product.

The coordinating investigator will report expedited the following SUSARs through the web portal *ToetsingOnline* to the METC:

- SUSARs that have arisen in the clinical trial that was assessed by the METC;
- SUSARs that have arisen in other clinical trials of the same sponsor and with the same medicinal product, and that could have consequences for the safety of the subjects involved in the clinical trial that was assessed by the METC.

The remaining SUSARs are recorded in an overview list (line-listing) that will be submitted once every half year to the METC. This line-listing provides an overview of all SUSARs from the study medicine, accompanied by a brief report highlighting the main points of concern.

The expedited reporting of SUSARs through the web portal *ToetsingOnline* is sufficient as notification to the competent authority. All participating centres receive SUSARs once a month by mail.

The expedited reporting will occur not later than 15 days after the coordinating physician has first knowledge of the adverse reactions. For fatal or life threatening cases the term will be maximal 7 days for a preliminary report with another 8 days for completion of the report.

In summary, patients report potential adverse effect/ event (AE) of the study drug to their own respiratory physician as well in their diary chart. The respiratory physician reports this adverse effect/event to the coordinating investigator within one week and in SAE (e.g. hospital admission) as soon as possible. The coordinating investigator will inform the METC as described before.

The list of randomisation will be stored at the department of Pulmonology of the Noordwest Ziekenhuisgroep, location Alkmaar. Breaking the code will only be performed by the coordination physician.

### **8.3 Annual safety report**

In addition to the expedited reporting of SUSARs, the sponsor will submit, once a year throughout the clinical trial, a safety report to the accredited METC, competent authority, and competent authorities of the concerned Member States.

This safety report consists of: a list of all suspected (unexpected or expected) serious adverse reactions, along with an aggregated summary table of all reported serious adverse reactions, ordered by organ system, per study; a report concerning the safety of the subjects, consisting of a complete safety analysis and an evaluation of the balance between the efficacy and the harmfulness of the medicine under investigation.

### **8.4 Follow-up of adverse events**

All AEs will be followed until they have abated, or until a stable situation has been reached. Depending on the event, follow up may require additional tests or medical procedures as indicated, and/or referral to the general physician or a medical specialist.

SAEs need to be reported till end of study within the Netherlands, as defined in the protocol.

### **8.5 Safety Committee/ Independent expert**

The safety committee consist of one member, called the independent expert who is independent of the set-up and execution of the trial. This independent expert will receive the definite protocol and all revisions. The independent expert will convene every three to six months and review the results, i.e. results split by experimental and control arms. The independent expert has the power to recommend termination of the study based on the evaluation of these results. There are typically three reasons an independent expert might recommend termination of the study: safety concerns, outstanding benefit, and futility. The primary mandate of this independent expert is to protect patient safety. If adverse events of a particularly serious type are more common in the experimental arm compared to the control arm, then the independent expert would have to strongly consider termination of the study. This evaluation has to be made in consideration of risk/benefit. In many cases, the experimental arm could cause serious adverse events, but the resulting improvement in survival could outweigh these adverse events.

The independent expert should inform the findings or conclusions to the study investigators by mail or e-mail. If there is any dispute between the independent expert and study investigators, the independent expert should notify the METC Noord-Holland.

The independent expert is:

[name] longarts, Heiloo

Email: [contact]

## 9. STATISTICAL ANALYSIS

### 9.1 Calculation of study numbers

See 4.4. sample size calculation

We used the Poisson regression model for the power analysis:

Numeric Results when X1 is Binomial with Proportion = 0,5 And Phi (Over-Dispersion Parameter) = 1,0000

	Mean R-Squared							
	Sample Size (N)	Response Rate Ratio	Baseline Rate Exp(B0)	Exposure Time (MuT)	X1 vs Other X's (R2)	Two-Sided Alpha	Beta	
Power	0,80000	36	0,5000	2,1000	1,0000	0,0000	0,05000	0,20000

The hypothesis is that prolonged treatment with tobramycin reduces the number of exacerbations per patient by 50%. This reduction seems clinical relevant and is based on the assumption that maintenance treatment with TIS OD as well as intermittent TIS BID is comparable to that of azithromycin treatment. This assumption is derived from the data of the BAT trial (placebo: mean 2,1 exacerbations (sd 1.6); azithromycin: mean 0,8 exacerbations (sd 1.1)). The reduction in percentage is used for the determination of trial size.

We used a poisson regression model to determine group size. For type I error and type II error 0.05 and 0.2 were used respectively. The hypothesis will be tested two sided. With a baseline exacerbation rate of 2.1 in the placebo group and an expected response rate ratio of 0.5 with an exposure time of 1 year a total of 18 evaluable patients are required to be on each treatment arm.

With a drop-out percentage of 30% we have to include totally 48 (24 patients per group) patients10:22. Due to unforeseen reasons we initially include two extra patients per group. But after the interim analysis three extra patients will be included in the study, because the drop-off percentage is higher as expected in advance. Reason for discontinuation of the study is the intensive treatment and cleaning schedule of the inhaled study medication. So with a total of 58 patients (29 per group) with bronchiectasis, and not the initially 52 patients (26 per group), we expect to achieve the intended effect size.

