Efficacy parameters will include assessment of pulmonary exacerbations, spirometry, LTRI-VAS, QOL-B and Leicester cough questionnaires. Microbiological response measurements will include semi-quantitative density of pathogens in sputum, including the tobramycin minimum inhibitory concentration (MIC) for isolated pathogens. Safety parameters will include assessment of AEs, serial spirometry findings, clinical laboratory test results, vital signs measurements, physical examination. Study drug is dispensed on the regular visits. The first patients will be enrolled in the summer of 2016, with a treatment period of 12 months, we expect to terminate the study 31-01-2020.

In subjects who experience a pulmonary exacerbation, every effort should be made to continue their allocated inhaled study drug, unless the study drug is not tolerated, or the pulmonary exacerbation is believed to be related to study drug. All subjects who receive any study drug need to complete the visit 7 assessments. Subjects who are prematurely withdrawn from study drug will be encouraged to

remain in the study and attend subsequent study visits; at a minimum, they should complete the visit 7 assessments as an early termination visit.

An independent expert will be established to conduct periodic reviews of subject safety for this protocol. The independent expert will also perform a blinded analysis of the pulmonary exacerbation data to check whether the assumptions for sample size estimation are valid, and if they are not, the sample size may be increased.

This study will be conducted in the Noordwest Ziekenhuisgroep, Canisius ZH Nijmegen, Spaarne Gasthuis Hoofddorp, Zuyderland MC Heerlen, VU Medical Center Amsterdam and UMC Utrecht.

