#### **9.4.3 Primary study parameter(s)**

A poisson regression model was used to analyse the primary outcome measure, evaluating both events and exposure (person-time), employing a quasilikelihood factor (with overdispersion correction), and incorporating the following covariables: treatment assignment, age, sex, smoking history, and presence of *P aeruginosa* and azithromycin maintenance use at baseline.

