#### **9.4.6 Interim analysis**

After inclusion and follow up of 50% of the randomized patients an interim analyses will be conducted. A poisson regression model is used for our power analysis; See chapter 9.1.

The interim analysis is used to calculate the predetermined effect size, and whether more patients should be included depending on this effect size. Depending on the frequency of exacerbations at baseline and the effect size, a power analyses will be done by using the poisson regression model.

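### The 80% power at 36 evaluable patients in section 9.1 assumes no over-dispersion; the SDs quoted beside it imply about 69% (66-75% across readings), and no power is stated for the current 58

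*Combined protocol and SAP*

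**What the plan says.** Section 9.1 (repeated in 4.4, apart from the program output) uses Poisson regression with a placebo rate of 2.1 per year, a rate ratio of 0.5, one year of exposure, two-sided alpha 0.05 and 1:1 allocation. The program output gives power 0.80 at N = 36, with "Phi (Over-Dispersion Parameter) = 1,0000". The rate comes from an azithromycin trial summarised as "placebo: mean 2,1 exacerbations (sd 1.6); azithromycin: mean 0,8 exacerbations (sd 1.1").

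Allowing for 30% drop-out and a few extra patients, the total was first 52. It is now 58, "because the drop-off percentage is higher as expected in advance". For 58 the text says only that "we expect to achieve the intended effect size".

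The primary analysis in 9.4.3 is a Poisson model "employing a quasilikelihood factor (with overdispersion correction").

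Two places revisit the sample size. Section 3 gives the independent expert a "blinded analysis of the pulmonary exacerbation data to check whether the assumptions for sample size estimation are valid". Section 9.4.6 says "A poisson regression model is used for our power analysis; See chapter 9.1", and then "Depending on the frequency of exacerbations at baseline and the effect size, a power analyses will be done by using the poisson regression model".

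**The concern.** Setting phi to 1 means that the variance of the counts equals their mean. The summary data quoted beside that setting show a variance above the mean in both arms, and the planned test widens its standard error by the estimated over-dispersion. The printed power is therefore not the power of the planned test on the plan's own source data.

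This is the only power figure in the plan. The move to 58 was made without a new one. The interim power calculation refers back to the 9.1 model and names only the exacerbation frequency and the effect size as inputs, so nothing there prompts a change of phi. The blinded check in section 3 could cover phi but does not name it.

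**Working it through.** **Inputs (section 9.1).** Placebo rate 2.1; rate ratio 0.5, so active rate 1.05; exposure 1 year; alpha 0.05 two-sided (z = 1.960); power 0.80 (z = 0.8416); allocation 0.5; source means and SDs 2.1 (1.6) and 0.8 (1.1).

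**Formula.** The plan's Poisson-regression formula, for N in person-years:

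N = (1.960·√V0 + 0.8416·√V1)² / (2.1·(ln RR)²)

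Power = Φ[(√(N·2.1·(ln RR)²) − 1.960·√V0) / √V1]

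At RR = 0.5, 2.1·(ln 0.5)² = 1.00895. With one common phi, V0 = 4·phi and V1 = 6·phi.

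**Reproducing the plan.** At phi = 1: N = (3.920 + 2.062)²/1.00895 = 35.46, rounded up to 36. Power at 36 = Φ[(6.027 − 3.920)/2.449] = 80.5%. This agrees with the printed output.

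**Over-dispersion in the quoted data.** Placebo 1.6²/2.1 = 1.219. Azithromycin 1.1²/0.8 = 1.5125. One-decimal rounding allows 1.55²/2.15 = 1.12 to 1.65²/2.05 = 1.33 for placebo, and 1.05²/0.85 = 1.30 to 1.15²/0.75 = 1.76 for azithromycin. Neither range reaches 1.

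**Each arm's own ratio.** The plan's formula takes one phi; this is its natural extension. V0 = 2(1.219) + 2(1.5125) = 5.463 and V1 = 2(1.219) + 4(1.5125) = 8.488. Power at 36 = Φ[(6.027 − 4.581)/2.913] = 69.0%.

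**Other readings.** All are for a 50% reduction. The 40.6 column is 58 × 0.7. The last column is 1 − N/58.

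| Phi, placebo / active | N for 80% | Power, 36 | Power, 40.6 | Power, 58 | Person-time loss at which 58 still gives 80% |
|---|---|---|---|---|---|
| 1 / 1 (plan) | 35.5 | 80.5% | 84.4% | 93.6% | 39% |
| 1.219 / 1.152 (SD 1.1 set against the planned mean: 1.21/1.05) | 41.9 | 74.6% | 78.9% | 89.9% | 28% |
| 1.219 / 1.219 | 43.2 | 73.5% | 77.8% | 89.0% | 25% |
| 1.219 / 1.5125 (each arm's own) | 49.0 | 69.0% | 73.4% | 85.4% | 15% |
| 1.219 / 1.67 (negative binomial) | 52.2 | 66.8% | 71.2% | 83.4% | 10% |
| 1.5125 / 1.5125 | 53.6 | 65.6% | 70.0% | 82.6% | 8% |

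The negative-binomial row takes k = 0.8²/(1.1² − 0.8) = 1.56 and 1 + 1.05/1.56 = 1.67 at the planned active mean.

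**Dilution.** With no person-time lost, 58 patients keep 80% power up to a diluted rate ratio of about 0.53 with each arm's own phi (0.51 at 1.5125 in both arms, 0.55 at 1.219 in both, 0.59 at phi = 1).

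**Source rate ratio.** 0.8/2.1 = 0.381. Power at 36 is 91% at phi 1.219 in both arms, 88% with each arm's own and 86% at 1.5125 in both.

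**The case against.** The plan's sum is correct and phi = 1 is printed openly, so this is an optimistic assumption and not a miscalculation. That is right: the fault lies in the choice of phi against the plan's own data.

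The inputs are crude. The SDs are marginal, one-decimal figures from a trial of another drug. The planned model uses person-time and baseline covariates, which could lower the residual phi. The active-arm ratio was seen at a mean of 0.8, while the plan assumes 1.05; moving it there can give 1.15 or 1.67 depending on the model. This stands, and is why a range is given. It does not support an unexplained 1, and every reading in the table puts power at 36 below 80%.

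The assumed effect is also cautious relative to the source, where power at 36 would be 86-91%. That stands too, but the stated hypothesis and the printed run are for a 50% reduction.

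A reader might infer that the trial of 58 is underpowered, or reaches 80% only if almost no person-time is lost. The documents support neither. Sections 7.3 and 7.6 require follow-up on the same schedule after treatment stops, and 9.3.1 keeps all randomised patients, so 30% contributing nothing is an extreme case. Section 3 does accept a single final visit as the minimum, so some loss is possible. If drop-outs contributed half a year on average (an assumption), the loss from 30% would be 15% and power about 80% with each arm's own phi, before dilution.

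Finally, the blinded check in section 3 could pick up phi, and 9.4.6 does not fix its value. Both are true, but neither text names phi.

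**Conclusion.** The point holds as a should-fix. Under the plan's own source SDs, power at 36 evaluable patients for a 50% reduction is about 69%, and about 66-75% across reasonable readings, against a stated 80%: roughly 5-14 points too high. A single figure for the excess would be more precise than these inputs allow.

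For the current 58, no power is stated. It is about 83-90% with a full year for everyone and about 70-79% if 30% contribute no person-time. It stays at 80% up to a person-time loss of about 15% with each arm's own phi (8-28% across readings), before any dilution of the effect. Whether 58 is enough depends on actual follow-up and dilution, which the plan does not state; it reports only that drop-out exceeds the assumed 30%.

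These figures rest on the plan's large-sample formula, on the quoted means and SDs, and on the source trial's dispersion carrying over to this one.

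**What to change.** In 4.4, 9.1 and 9.4.6, with a matching line in section 3:

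1. Replace phi = 1 with a justified value or range (about 1.2 to 1.5, marked approximate), or with the blinded estimate from the check in section 3. A pooled blinded variance/mean also contains the difference between arms, about ((2.1 − 1.05)/2)²/1.575 = 0.18 if the rates are as planned, so state whether that is removed.
2. Name phi among the assumptions that the blinded check covers, and use the resulting value in the interim power calculation.
3. Restate power at 36, and at 58 on expected intention-to-treat person-time, giving the assumed follow-up after drop-out and the assumed dilution.
4. Put that figure in place of "we expect to achieve the intended effect size", since the number of patients determines power and not the size of the effect.

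The cost is some wording, one re-run of the power program and a less favourable stated power. Whether to enlarge the trial remains the sponsor's decision.

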### **7.6 Follow-up of subjects withdrawn from treatment**

Follow-up of patients withdrawn from treatment have an out-patient visit following the study schedule. These patients will be evaluated the same as the patients who complete the study. Subjects will be evaluated at run-in = visit 0 (week -4), visit 1 (day 1- start of the study), visit 2 (week 13), visit 3 (week 26), visit 4 (week 39), visit 5 (week 52: end of treatment) and visit 6 (run-out; week 56: end of the study). One week after start of treatment a phone call will be scheduled. During an exacerbation the patient will contact his/her own GP or specialist.

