#### **9.3.3 Per protocol Treatment analysis (PTT)**

All randomized patients who received and completed treatment according to study protocol will be included in the per protocol analysis. Patients will be considered as non-evaluable if they do not complete a total treatment for at least 9 months. Termination of the study or incomplete data collection is also defined as non-evaluable.

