### **9.4 Methods of analysis**

#### **9.4.1 General statistical considerations**

All data will be collected and analysed using SPSS statistics 20.

Statistical analysis will be performed on an intent-to-treat basis by the investigator and an independent statistician. All continuous variables will be tested for normal distribution with the Kolmogorov-Smirnov test for normal distribution. The Student-t test will be used for normally distributed variables, the Mann-Whitney U test for not normally distributed variables and the  $\chi^2$  test for dichotomous variables. The software package SPSS 20 for Windows (IBM-SPSS Inc., Chicago, Illinois, USA) is available for statistical analysis. A value of  $p < 0.05$  will be considered significant.

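### The stated 80% power is for 36 evaluable patients, not for the planned intention-to-treat comparison of all 58 randomised patients, for which no power is given

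*Combined protocol and SAP*

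**What the plan says.** Section 9.1, repeated in 4.4, sets the sample size with a Poisson regression formula. The error rates are given as "For type I error and type II error 0.05 and 0.2 were used respectively", and "The hypothesis will be tested two sided". The placebo rate is taken as 2.1 exacerbations a year. The remaining inputs and the result read: "expected response rate ratio of 0.5 with an exposure time of 1 year a total of 18 evaluable patients are required". This number is per arm, so 36 in all. The software output in 9.1 shows "Phi (Over-Dispersion Parameter) = 1,0000".

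A 30% drop-out allowance then raises enrolment to 24 per group. Two more per group are added for unforeseen reasons, and three more because drop-out proved higher than expected, giving 29 per group and 58 in total.

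The only definition bearing on the word evaluable is in the per-protocol section, 9.3.3: "Patients will be considered as non-evaluable if they do not complete a total treatment for at least 9 months".

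The analysis uses a different population. Section 9.4.1 says: "Statistical analysis will be performed on an intent-to-treat basis by the investigator and an independent statistician". Section 9.3.1 puts every randomised patient in the intention-to-treat set. Section 7.3 has patients who end treatment followed for as long as those who complete, and 7.6 says of them: "These patients will be evaluated the same as the patients who complete the study". Section 9.4.3 specifies a Poisson model with person-time and an overdispersion correction but names no population, so the general rule in 9.4.1 governs.

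**The concern.** The sample-size calculation treats patients who drop out as simply absent: they add no information and do no harm to the effect. In the planned analysis they are present. A tobramycin patient who stops early and is followed to week 52 contributes off-drug exacerbations and person-time to the tobramycin arm. That pulls the rate ratio towards 1. Enrolling more patients replaces lost person-time but cannot undo this pull, although the closing sentence of 9.1 expects the intended effect size to be achieved with 58.

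No section lowers the assumed effect for stopping or states power for the all-randomised comparison. If readers carry the 80% over to that comparison, a non-significant result could be taken as stronger evidence against a halving of exacerbations than the design can give. Section 9.1 itself attributes the higher drop-out to the burden of inhaling and cleaning, so stopping treatment is a live issue in this trial.

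**Working it through.** **Inputs from 9.1:** two-sided alpha 0.05 (z = 1.960), power 80% (z = 0.8416), placebo rate 2.1 per year, rate ratio RR = 0.5, exposure T = 1 year, phi = 1, equal allocation. **From sections 3 and 9.1:** 58 randomised, 29 per arm, drop-out allowance 30%.

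**1. Reproduce the plan.** With half the patients in each arm, the cited formula is

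N = phi × [1.960 × √4 + 0.8416 × √(2 + 2/RR)]² / (2.1 × T × (ln RR)²).

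At RR = 0.5: (3.920 + 2.062)² / (2.1 × 0.4805) = 35.78 / 1.009 = 35.46, so 36. This matches the plan. Power at 36 is 80.5%.

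**2. Solve the same formula for power at 58.**

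z(power) = [√(58 × 2.1 × T / phi) × |ln RR| − 3.920] / √(2 + 2/RR).

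With no dilution (RR = 0.5, T = 1, phi = 1), power is 94%.

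**3. Stoppers stay in follow-up, as 7.3 and 7.6 plan.** The documents give no stopping times and no rate after stopping, so the following are assumptions: 0.5 applies while on drug, the off-drug rate equals placebo, and everyone is followed for the year. If a share d of the tobramycin arm stops after a fraction f of the year,

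RR(ITT) = 0.5 × (1 − d) + d × [0.5f + (1 − f)] = 0.5 + 0.5 × d × (1 − f).

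With d = 0.30 and phi = 1:

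| Time of stopping | RR(ITT) | z(power) at 58 | Power at 58 |
|---|---|---|---|
| Day 1 (f = 0) | 0.65 | (4.754 − 3.920)/2.253 = 0.370 | 64% |
| 3 months (f = 0.25) | 0.6125 | (5.410 − 3.920)/2.295 = 0.649 | 74% |
| 6 months (f = 0.5) | 0.575 | (6.107 − 3.920)/2.341 = 0.935 | 82% |

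Setting power to 80% and solving for the ratio, 58 patients suffice only while RR(ITT) is no higher than about 0.585.

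**4. Stoppers leave the study when they stop.** RR stays at 0.5 but person-time falls. With 30% leaving, person-years are 58 × 0.70 = 40.6 (day 1) to 58 × 0.85 = 49.3 (mid-year), and power is 84% to 90%.

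**5. Overdispersion.** The placebo figures quoted in 9.1 (mean 2.1, SD 1.6) imply a variance-to-mean ratio of 1.6²/2.1 = 1.22. With phi = 1.22, the step 3 range falls from 64%–82% to 57%–75%. A 20,000-run simulation of a quasi-Poisson test without covariates, on Poisson counts with 29 per arm and 30% stopping, gives 50% (day 1) to 72% (mid-year), and 89% with no stopping. The cited formula is therefore somewhat optimistic at this size.

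**The case against.** **A reader might infer that the trial is underpowered.** The documents do not show this. Sections 3 and 5.3 only encourage patients who stop drug to stay, and accept an early termination visit as the minimum. Section 7.3 removes tolerance-test failures from the study, and 9.1 speaks of stopping the study rather than the drug. On that reading step 4 applies and power exceeds 80%. Even with full follow-up, 30% stopping at mid-year leaves 82%. This part of the objection stands: a shortfall needs early stopping, good retention and loss of effect after stopping, and the documents settle none of these.

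**A reader might take 0.5 as the on-treatment ratio.** The plan never says so. Its source figures, 0.8 against 2.1, give 0.38, so 0.5 is already weaker than its source. Starting from 0.38 with 30% stopping, the ratio is 0.38 + 0.62 × 0.30 = 0.57 (day 1) to 0.38 + 0.62 × 0.15 = 0.47 (mid-year), with power at 58 of 84% to 96%. The plan does not give this as its reason for 0.5, and whether the source figures were intention-to-treat cannot be seen from the documents. The sponsor has to say which ratio 0.5 is.

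**A reader might combine the 9-month rule in 9.3.3 with the assumed year of exposure and conclude that exposure is overstated.** That rule is a minimum treatment duration for the per-protocol set. The model in 9.4.3 uses person-time, and a stopper followed to week 52 supplies about a full year.

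**A reader might work back from 36 evaluable out of 58 to an implied drop-out of 38%.** The 58 includes four patients added for unforeseen reasons, so no drop-out rate can be read from it. The revised rate is not stated.

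None of this removes the mismatch: the 80% is tied to evaluable patients, and the intention-to-treat test has no stated power.

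**Conclusion.** The point holds as a mismatch between the population that was powered and the population that will be analysed. It is not an arithmetic error, since the plan's 36 reproduces. Under the assumptions of step 3, 30% stopping puts power at 58 between 64% and 82% with phi = 1, and lower if overdispersion is allowed for. If stoppers leave the study, it is about 84% to 90% with phi = 1. The stated 80% applies to neither case except by coincidence. Whether true power lies above or below it depends on the meaning of 0.5, when patients stop, what happens to their rate afterwards and whether they are really followed, all of which the plan leaves open or states inconsistently.

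**What to change.** In 4.4 and 9.1:

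- State power at 58 for the all-randomised comparison, in place of power for 36 evaluable patients.
- Say whether 0.5 is the intention-to-treat ratio or the ratio while on treatment. If the latter, give the resulting intention-to-treat ratio.
- Give the assumed share and timing of stopping, and the rate assumed afterwards, as a labelled range.
- Use an overdispersion value consistent with the correction planned in 9.4.3 instead of phi = 1, and preferably confirm the result by simulating the planned test.

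Name the analysis population for the primary model in 9.4.3. Reconcile 7.3 and 7.6 with sections 3 and 5.3 on follow-up after stopping, and the removal of tolerance-test failures in 7.3 with their place in the intention-to-treat set under 9.3.1.

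The cost is rewording and a short recalculation. Enrolment stays at 58. The stated power may become less favourable.

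### The 80% power stated for 18 evaluable patients per arm is about 71–72% for the Poisson test on the plan's own inputs, and lower once the five covariates are fitted

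*Combined protocol and SAP*

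**What the plan says.** Section 9.1, repeated in substance in 4.4, sets the inputs. "For type I error and type II error 0.05 and 0.2 were used respectively", and "The hypothesis will be tested two sided". The placebo rate is fixed by "With a baseline exacerbation rate of 2.1 in the placebo group". The assumed effect and the follow-up time are given as "an expected response rate ratio of 0.5 with an exposure time of 1 year". The software output in 9.1 is headed "Numeric Results when X1 is Binomial with Proportion = 0,5" and "Phi (Over-Dispersion Parameter) = 1,0000". Its row shows N = 36, power 0.80, and an R-squared of zero between treatment and the other covariates. The conclusion is that "a total of 18 evaluable patients are required to be on each treatment arm".

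The later totals start from that figure: 48 after a 30% drop-out allowance, 52 with two extra patients per group, and 58 (29 per group) after the interim analysis because drop-out was higher than expected.

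Section 9.4.3 plans a quasi-likelihood Poisson model with over-dispersion correction, "incorporating the following covariables: treatment assignment, age, sex, smoking history", plus *P. aeruginosa* and azithromycin use at baseline. That is treatment and five covariates. Section 9.4.6 refers the interim power calculation back to 9.1.

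**The concern.** The stated power should describe the test that will be run. When the drug works as assumed, the data come from rates 2.1 and 1.05, and the test takes its standard error from those data. A formula that puts both arms at 2.1 in its null term assumes more events than will occur, so it sets the significance boundary too close to a rate ratio of 1 and reports too much power. Zero R-squared also leaves out the precision lost by fitting five covariates to 36 patients.

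A non-significant result at the planned evaluable number would be read against a 20% type II error when the figure is nearer 28–29% before adjustment. Because 9.4.6 points back to 9.1, the same optimism would enter any re-estimation, even one that updates the other inputs.

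**Working it through.** **Inputs (9.1):** alpha 0.05 two-sided; power 0.80; placebo rate 2.1; rate ratio 0.5, so active rate 1.05; exposure 1 year; allocation P = 0.5; phi = 1; R² = 0.

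**1. Reproducing 36.** The Poisson-regression formula is

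N = phi × (1.960√V0 + 0.8416√V1)² / [T × 2.1 × (ln 0.5)² × (1 − R²)],

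with V1 = 1/(1 − P) + 1/(P × 0.5) = 2 + 4 = 6. With both arms at 2.1 under the null, V0 = 1/(P(1 − P)) = 4. Then (1.960 × 2 + 0.8416 × 2.449)² = 5.981² = 35.78. The denominator is 2.1 × 0.4805 = 1.009. N = 35.46, rounded up to 36, which matches.

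**2. Other null variances.** At N = 36, √(36 × 1.009) = 6.027 and power = Φ[(6.027 − 1.960√V0)/√6].

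| Null term | V0 | N for 80% | Power at 36 |
|---|---|---|---|
| Both arms at 2.1 | 4 | 35.46 → 36 | 80.5% |
| Both arms at pooled rate 1.575 | 4 × 2.1/1.575 = 5.33 | 43.0 → 44 | 73.0% |
| Wald, alternative variance throughout | 6 | 46.7 → 47 | 69.2% |

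Only the first gives 36.

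**3. Why the first is too favourable.** Null standard errors of the log rate ratio at 18 per arm, and the rate ratio each would just declare significant, exp(−1.96 × SE):
- formula: √(4/75.6) = 0.230, limit 0.637;
- pooled: √(4/56.7) = 0.266, limit 0.594;
- Wald: √(1/37.8 + 1/18.9) = 0.282, limit 0.576.

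**4. Power by enumeration.** For the unadjusted test at phi = 1, power follows from two Poisson totals with means n × 2.1 and n × 1.05, with no simulation.

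| n per arm | Wald | Score | Likelihood ratio |
|---|---|---|---|
| 18 | 71.0% | 71.7% | 72.1% |
| 20 | 75.7% | 76.3% | 76.7% |
| 22 | 79.6% | 80.3% | 80.5% |
| 23 | 81.4% | 82.0% | 82.2% |
| 29 | 89.4% | 89.8% | 89.8% |

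Type I error at 18 per arm is 4.8–5.1%, so the gap does not come from a conservative test. Simulating the quasi-likelihood version without covariates gives 70.9% (z reference) and 68.4% (t reference).

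**5. Five covariates.** With 36 patients, chance correlation of treatment with five unrelated covariates averages R² = 5/35 = 0.14. Putting that in the formulas of step 2 gives 62.5% (Wald) to 66.6% (pooled). Simulation, 6,000 runs per setting, assumed one normal and four binary covariates with no effect on the outcome:
- Poisson Wald 63.1%, likelihood ratio 64.6%;
- quasi-likelihood 63.0% (z), 59.8% (t).

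A log rate ratio of 0.2 per covariate gave 61–66%.

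**6. The 58 randomised (phi = 1).**
- 30% lost and contributing nothing: 29 × 0.7 = 20.3, about 20 per arm, 76–77% unadjusted and lower when adjusted.
- Keeping 22–23 of 29 evaluable means losing only 1 − 22/29 = 24% to 1 − 23/29 = 21%.
- All followed for one year: 89–90% unadjusted, 85–87% adjusted.

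**The case against.** **This is not a calculation slip.** 9.1 reports software output for a named, published method, and 36 is what that formula gives. That is fair: the fault lies in applying the formula to this test, not in the arithmetic. The formula is also inferred from the match to 36, because the documents print neither it nor its null variance. The inference is strong, since the alternatives give 44 and 47, but it should be stated as one.

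**The null variance is legitimate under the null.** If treatment has no effect, both arms do share the placebo rate. This does not help the power figure, which concerns data generated under the alternative.

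**A reader might infer that the trial as now planned lacks 80% power.** The documents do not support that. The plan randomises 58, analyses by intention to treat (9.3.1, 9.4.1), models person-time (9.4.3), and follows patients who stop treatment on the full schedule (7.3, 7.6). With complete follow-up and phi = 1, power exceeds 80% even after adjustment. The protocol nevertheless plans by evaluable patients and says drop-out exceeded the 30% allowed. On that basis 58 does not restore 80%, and no calculation for partial follow-up is given.

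**The adjusted figure depends on assumptions.** 9.4.3 gives neither covariate distributions nor coding; smoking history, for example, could take more than one term. This objection stands, so 59–65% is a range under stated assumptions. The 71–72% figure needs none of them.

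**Conclusion.** The concern holds for the evaluable-patient target. On the plan's own rates, with phi = 1 and a full year of exposure, 18 per arm gives about 71–72% power for the unadjusted Poisson test, 8–9 points below the stated 80%; 22–23 evaluable per arm would be needed. With five non-prognostic covariates of one term each, power is roughly 59–65%, depending on the test and its reference distribution. No other section corrects the statement.

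The finding does not extend to an intention-to-treat analysis of all 58. There the answer depends on follow-up, running at phi = 1 from about 76–77% unadjusted, if 30% contribute nothing, to about 85–87% adjusted and 89–90% unadjusted, if everyone completes a year.

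**What to change.** In 4.4 and 9.1, replace the 80% with about 71% for 36 evaluable patients, and name the method. Power should be computed for the test in 9.4.3, by simulation or from SE(log rate ratio) = √(phi/(n × 2.1) + phi/(n × 1.05)). The closed form is slightly conservative (69% against an enumerated 71% at 18 per arm), so state which was used. Give the figure with the five covariates as a range, with the assumed coding.

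Report power for 29 per arm by the same method, as a range over stated drop-out and exposure assumptions. In 9.4.6, specify this method for any re-estimation in place of the reference back to 9.1.

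The cost is a few sentences, a short simulation, and a less favourable stated power. No extra enrolment is proposed, and the primary analysis does not change.
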